- ^a In case of rescue therapy, all assessments planned in V12 should be performed before starting rescue therapy, patients then continue the study treatment (including metformin), and all visits and assessments should be performed as scheduled. In case of premature permanent IMP discontinuation, patients should have a visit as soon as possible with the assessments normally planned in V12 (the standardized meal test and PK collections are performed only if the patient receives the IMP the day of the visit, note that otherwise predose PK sample can be taken if the patient receives the IMP the day before). Afterward, the patients should continue in the study up to the scheduled date of study completion. They should be followed up according to the study procedures as specified in the protocol (except for the 3 day safety post-treatment and PK assessment). If the patient drops out from the study at the time of IMP discontinuation regardless if the patient receives the IMP or not on the day of the meal test, the meal test should be performed. However, PK collections are performed only if the patient receives the IMP the day of the visit, otherwise predose PK sample can be taken if the patient receives the IMP the day before.
- ^b Weight will be recorded to the nearest 0.1 kg and should be measured using calibrated scales. The same pair of scales should preferably be used throughout the trial. Weight should be measured in the fasting state in the morning at approximately the same time with an empty bladder, without shoes and only wearing undergarments or light clothing. Weight measured at screening Visit 1 will be used only for calculation of screening BMI for eligibility criteria whereas weight measured at Visit 4 will be used as baseline for assessment of change in body weight and for calculation of baseline BMI which will be the BMI value used for stratification.

- c* At Visit 9, abbreviated/targeted physical examination only.
- d* Diary will be reviewed at each on site visit.
- e* Counseling will be provided at screening Visit 3 or Visit 4.
- f* Only for patients in SAR425899 or Placebo arms.
- g* First dose of IMP will be done on-site .IMP administration every day along the 26-weeks, but at each visit on site, the IMP administration will be done on site by the patient himself.
- h* 7-point profile to be conducted over a single 24-hour period in the week before Visit 4, Visit 10 and Visit 12.

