#### 2.1.4 Safety endpoints

The safety endpoints are assessed by:

- Adverse events (AEs), serious adverse events (SAEs), AE of special interest (AESIs), hypoglycemia (severe, documented, asymptomatic, probable, relative), vital signs, ECG changes, and safety laboratory values,
- Change of heart rate from baseline to Week 26 by ECG,
- Change of heart rate from baseline to Week 26 by Holter monitor in up to 50% subset of all patients,
- Antibody assessments: anti-SAR425899 antibodies samples will be collected in all patients (except patients on Liraglutide) at baseline, Week 2, Week 4, Week 14, and Week 26 before dosing. Patients will be asked to provide sample for anti-SAR425899 antibodies assessments 3 months after the end of the study if needed.

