#### *Observation period*

The observation period will be divided into 4 epochs:

- The **screening** epoch is defined as the time from the signed informed consent date up to the first administration of the IMP.
- The **treatment** epoch is defined as the time from the first administration of the IMP to the last administration of the IMP
- The **residual treatment** epoch is defined as the time from the last administration of the IMP up to 3 days (1 day for hypoglycemia, 28 days for anti-SAR425899 antibody) after the last administration of IMP.

The treatment-emergent adverse event (TEAE) period will include both **treatment** and **residual treatment** epochs.

- The **posttreatment** epoch is defined as the period of time starting the day after the end of the treatment-emergent adverse event period up to the end of the study (defined as last protocol-planned visit or the resolution/stabilization of all serious adverse events (SAE) and adverse events with prespecified monitoring as defined in protocol).

The on-study observation period is defined as the time from the start of treatment until the end of study (defined as the last scheduled visit for those who completed the study and the date collected on e-CRF page “Completion of End of Study/Follow-up” for those who did not complete the study, or the resolution/stabilization of all serious adverse events and adverse events with prespecified monitoring as defined in the protocol whichever is the latest).

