### **2.4.5.1 Analyses of hypoglycemia**

Analyses of hypoglycemia will be performed on the TEAE period, as defined in [Section 2.1.4](#). Hypoglycemia will be classified as severe hypoglycemia, documented symptomatic hypoglycemia, asymptomatic hypoglycemia, probable symptomatic hypoglycemia or relative hypoglycemia (see [Section 2.1.4.1](#)).

The number (%) of patients with any hypoglycemia, severe hypoglycemia and documented symptomatic hypoglycemia will be summarized respectively by treatment group for the TEAE period, as well as the incidence rate in patient years. Two types of incidence rates will be presented: the number of patients with at least 1 event per patient years (calculated as the number of patients with at least 1 event / total exposure in patient years), and the number of events per patient years (calculated as the number of events / total exposure in patient years). Note: here exposure is duration of TEAE period, ie, duration of IMP treatment in days +1 (see [Section 2.1.4](#)).

The summary of frequency and incidence rate in patient years for severe hypoglycemia or documented symptomatic hypoglycemia will be provided as appropriate by gender (Male, Female), age group (<50, ≥50 to <65, ≥65 to <75, ≥75 years of age), race (American Indian or Alaska Native, Asian/Oriental, Black, Native Hawaiian or Other Pacific Islander, White, Other).

The summary of frequency and incidence rate in patient years for severe hypoglycemia or documented symptomatic hypoglycemia will be provided as appropriate by anti-SAR425899 antibody status (Positive, Negative) during TEAE period. A patient is defined as anti-SAR425899 antibody positive during the TEAE period if the patient is anti-SAR425899 antibody positive at any time during TEAE period, ie, duration of IMP treatment in days +28 (see [Section 2.1.4](#)).

A KM curve will also be provided by treatment group for the time to first onset of severe or documented symptomatic hypoglycemia during the TEAE period.

A listing of patients for all hypoglycemic events reported on the dedicated eDiary or eCRF “Hypoglycemic Event Information” form will be provided with each category flagged (ie, severe hypoglycemia, documented symptomatic hypoglycemia, asymptomatic hypoglycemia, probable symptomatic hypoglycemia and relative hypoglycemia).

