- Summaries of common TEAEs (PTs with an incidence  $\geq 3\%$  in any treatment group) will be provided as appropriate for SAR425899 treatment groups by primary SOC, HLGT, HLT, and PT and by anti- SAR425899 antibody status (Positive, Negative) during the TEAE period as necessary. SOC will be sorted by internationally agreed order and the other levels (HLGT, HLT, PT) in alphabetic order.

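### Hypoglycemia and common adverse events are split by ever-positive antibody status, a label set after baseline, so the comparison can mislead in either direction (minor)

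*SAP*

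**What the plan says.** SAP 2.4.5.1 plans frequencies and incidence rates for severe or documented symptomatic hypoglycemia, which "will be provided as appropriate by anti-SAR425899 antibody status (Positive, Negative) during TEAE period". A patient is positive "if the patient is anti-SAR425899 antibody positive at any time during TEAE period", and the section spells out the window as "duration of IMP treatment in days +28". This agrees with SAP 2.1.4 (Observation period), where the residual window is 3 days in general but "1 day for hypoglycemia, 28 days for anti-SAR425899 antibody". The event rate is "the number of events / total exposure in patient years", so a patient's whole exposure goes with the label.

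SAP 2.4.5.2 (Analysis of all treatment-emergent adverse events) splits common events in the SAR425899 groups by "antibody status (Positive, Negative) during the TEAE period as necessary". It does not repeat the definition. Its percentages use patients in the safety population as denominator, with no adjustment for exposure.

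Samples are planned "at baseline, Week 2, Week 4, Week 14, and Week 26 before dosing". For early stoppers, the footnote to the flow chart in Protocol 1.2 adds: "In case of premature permanent IMP discontinuation, patients should have a visit as soon as possible with the assessments normally planned in V12". The Visit 12 assessments include the antibody sample.

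Neither document plans a landmark, time-dependent or before-and-after-seroconversion analysis.

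**The concern.** To be labelled positive, a patient must seroconvert and be sampled afterwards within the window, which favours patients who stay on treatment. Events count from the first dose. This produces two distortions that pull in different directions.

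- If events cause stopping, patients with events tend to leave before a positive sample and are counted as negative. Antibodies then look protective.
- If events are unrelated to stopping, positive patients simply have longer follow-up and more time to have an event. On a percentage that ignores exposure, antibodies then look harmful.

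In both cases an event before the first positive sample is credited to the positive group if the patient converts later.

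Safety together with immunogenicity is a main secondary objective (SAP 1.2.2), and these are the only planned tables that set antibody status against clinical events. A false association in either direction, or a true one hidden, would be easy to misread.

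**Working it through.** The plan states no figure to reproduce. The documents give the status rule, the window and the sampling weeks. Seroconversion, event and stopping rates are not in the documents and are assumptions throughout.

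**Which samples count for an early stopper.** Take a stop at Day 21. The window ends at Day 21 + 28 = Day 49. The Week 2 sample (Day 14), the stop-visit sample and, if the patient stays in the study, the Week 4 sample (Day 28) all count. Week 14 (Day 98) does not. Such a patient has up to three samples, all early.

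**Direction by simple arithmetic.** Assume 15% stop early; 50% of completers and 10% of stoppers are ever positive; 30% of completers have nausea whatever their status; a share x of stoppers have nausea.

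- Positive: (0.85×0.5×0.3 + 0.15×0.1×x) / (0.85×0.5 + 0.15×0.1) = (0.1275 + 0.015x) / 0.44
- Negative: (0.85×0.5×0.3 + 0.15×0.9×x) / (0.85×0.5 + 0.15×0.9) = (0.1275 + 0.135x) / 0.56

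| x | Positive | Negative | Negative minus positive |
|---|---|---|---|
| 100% | 32.4% | 46.9% | +14.5 points |
| 50% | 30.7% | 34.8% | +4.1 points |
| 30% | 30.0% | 30.0% | 0 |
| 15% | 29.5% | 26.4% | −3.1 points |

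The sign turns on how strongly events and stopping are linked.

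**Simulation with no antibody effect** (400,000 patients per scenario). Assumptions: antibody onset uniform over Weeks 1 to 20; mean 0.5 events per 26 weeks; events either constant over time, or front-loaded (60% placed in Weeks 0 to 4, the rest spread over 26 weeks); background stopping 10% unless stated, half of it in Weeks 0 to 4; 40% seroconvert unless stated. Samples are at Weeks 2, 4, 14 and 26 plus the stop visit, with the 28-day window. Ratios are positive over negative under the SAP rule; the true value is 1.00.

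| Events | Events causing stopping | Rate ratio | Frequency ratio |
|---|---|---|---|
| Constant | 0% | 1.00 | 1.08 |
| Constant, 30% background stopping | 0% | 1.01 | 1.26 |
| Front-loaded | 0% | 0.97 | 1.04 |
| Constant | 30% | 0.83 | 0.94 |
| Front-loaded | 10% | 0.86 | 0.96 |
| Front-loaded | 30% | 0.67 | 0.81 |
| Front-loaded, 20% seroconvert | 30% | 0.72 | 0.84 |
| Front-loaded, 60% seroconvert | 30% | 0.58 | 0.76 |

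Across these scenarios:

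- Patients stopping before Week 4 are ever positive in 3 to 10%, against 17 to 52% overall.
- 14 to 41% of Week 0 to 4 events nevertheless sit in the positive group.
- 58 to 83% of the positive group's events precede its first positive sample.
- Omitting the stop-visit sample moves the ratios by at most about 0.04.

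**Alternatives under the same null.**

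- Landmark (status through Week 4 or Week 14, later events and person-time, patients still on treatment): 0.98 to 1.02.
- Status switched at the first positive sample, stratified by study period: 0.98 to 1.02.
- Status switched at the first positive sample, unstratified, front-loaded events: 0.35 to 0.41. Early weeks carry most events and almost no positive person-time, so this is further from 1 than the SAP rule.

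**The case against.** The strongest reply is that little depends on these tables. They are optional by their own wording, the safety analysis is descriptive without systematic testing (SAP 2.4.5, General common rules), and no decision rule uses them. Onset dates and study days are listed (SAP 2.4.5.2), as is antibody status (SAP 2.4.5.8), so a careful reader could rebuild the timing. The hypoglycemia summary already includes an exposure-adjusted rate, and nothing in the documents suggests that hypoglycemia drives stopping. All of this stands and sets the severity. It does not make a table unbiased once it is produced.

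Two stronger readings are tempting. A reader might infer that early events as such fall into the negative group. They do not: an early event in a patient who later converts is counted as positive. A reader might also infer that antibodies will look protective. That needs events that lead to stopping. Protocol 8.1.1 makes the link plausible for poor tolerability such as nausea and vomiting, since intolerance can end in discontinuation of the study drug, but no rate is given. The 14.5-point gap above requires every early stopper to have had nausea; at 50% it is 4.1 points, and at the completers' 30% it is zero.

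**Conclusion.** The concern holds as a minor point. The ever-positive rule compares groups formed by what happened after the first dose, and the result is biased in a direction that cannot be known in advance. With no true effect and the assumptions above, the rate ratio runs from 0.58 to 1.01 and the frequency ratio from 0.76 to 1.26. The low ends need front-loaded events that often cause stopping. The high end of the frequency ratio needs substantial stopping unrelated to events. For hypoglycemia, where no link to stopping is documented, the rate should be close to unbiased, and the percentage is the figure more likely to mislead. For gastrointestinal events the protective direction is more plausible. The documents do not support claiming either direction as the expected result.

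**What to change.** In SAP 2.4.5.1 and 2.4.5.2, replace or supplement the split by ever-positive status with one of the following:

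1. **Landmark analysis (simpler).** Class patients still on treatment by antibody status through Week 4 and, separately, through Week 14. Count only events with later onset and person-time after the landmark.
2. **Time-dependent status.** Count events and person-time as negative until the first positive sample and positive from then on, and stratify the comparison by study period, for example Weeks 0–2, 2–4, 4–14 and 14–26.

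Do not use the second option without the strata.

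The SAP should also say how a patient with no post-baseline antibody sample is classed; the antibody sections are silent on this.

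The cost is SAP wording and programming on dates already collected. The downside of the landmark is fewer events: in the front-loaded scenario only 0.4 × 22/26 = 34% of events fall after Week 4 and 0.4 × 12/26 = 18% after Week 14, before allowing for stopping. The existing overall tables would still show the earlier events.

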### **2.4.5.2 Analyses of adverse events**

#### ***Generalities***

The primary focus of AE reporting will be on treatment-emergent adverse events (TEAEs). Pre- and post-treatment AEs will be described separately.

If an AE date/time of onset (occurrence, worsening, or becoming serious) is incomplete, an imputation algorithm will be used to classify the AE as pre-treatment, treatment-emergent, or post-treatment. The algorithm for imputing date/time of onset will be conservative and will classify an AE as treatment-emergent unless there is definitive information to determine it is pre- or post-treatment. Details on classification of AEs with missing or partial onset dates are provided in [Section 2.5.3](#).

Adverse event incidence tables will be presented by SOC, HLGT, HLT, and PT, sorted by the internationally agreed order for SOCs and alphabetic order for HLGT, HLT and PT within a SOC, the number (n) and percentage (%) of patients experiencing an adverse event. Multiple occurrences of the same event in the same patient will be counted only once in the tables within a treatment phase. The denominator for computation of percentages is the safety population within each treatment group.

Sorting within tables ensures the same presentation for the set of all adverse events within the observation period (pretreatment, treatment-emergent, and posttreatment). For that purpose, the table of all treatment-emergent adverse events presented by primary SOC and PT (sorted by the internationally agreed SOC order and decreasing frequency of PTs within SOCs in the SAR425899 0.20 mg group) will define the presentation order for all other similar tables unless otherwise specified. In case of equal frequency regarding PTs, alphabetical order will be used.

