6.2 DURATION OF STUDY PARTICIPATION

6.2.1 Duration of study participation for each patient

The study comprises 3 periods as described below (please see the graphical study design and study flowchart in [Section 1.1](#) and [Section 1.2](#), respectively):

- A 3-week screening period,
- A 26-week treatment period,
- And a 3-day post treatment follow-up period.

The total duration of the study will be approximately 30 weeks for each patient.

A detailed description of the assessments performed in each study period is provided in [Section 10.1](#).

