9.2.2.1 Observation period of safety endpoints

The observation period of safety data will be divided into 3 segments:

- The pretreatment period is defined as the time between the date of the informed consent and the first injection of IMP.
- The on-treatment period is defined as the time from the first injection of IMP up to 3 days (1 day for hypoglycemia) after the last injection of IMP, regardless of the introduction of rescue therapy. The 3-day interval is chosen based on the half-life of the IMP (approximately 5 times the half-life of SAR425899).
- The post treatment period is defined as the time starting 4 days after last injection of IMP (after the on-treatment period).

The baseline value for safety endpoints will be the last available value prior to the first injection of IMP.

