10.4.3 General guidelines for reporting adverse events

- All AEs, regardless of seriousness or relationship to IMP/NIMP, spanning from the signature of the informed consent form until the end of the study as defined by the protocol for that patient, are to be recorded on the corresponding page(s) or screen(s) of the eCRF.
- Whenever possible, diagnosis or single syndrome should be reported instead of symptoms. The Investigator should specify the date of onset, intensity, action taken with respect to IMP, corrective treatment/therapy given, additional investigations performed, outcome, and his/her opinion as to whether there is a reasonable possibility that the AE was caused by the IMP or by the study procedure(s).
- The Investigator should take appropriate measures to follow all AEs until clinical recovery is complete and laboratory results have returned to normal, or until progression has been stabilized, or until death, in order to ensure the safety of the patients. This may imply that

observations will continue beyond the last planned visit per protocol, and that additional investigations may be requested by the monitoring team up to as noticed by the Sponsor.

- When treatment is prematurely discontinued, the patient's observations will continue until the end of the study as defined by the protocol for that patient.
- Laboratory, vital signs or ECG abnormalities are to be recorded as AEs only if:
 - Symptomatic and/or,
 - Requiring either corrective treatment or consultation, and/or,
 - Leading to IMP discontinuation or modification of dosing, and/or,
 - Fulfilling a seriousness criterion, and/or,
 - Defined as an AESI.

Instructions for AE reporting are summarized in [Table 6](#).

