### **2.3.2 Safety population**

Safety analyses will be based on the safety population, defined as all randomized patients who receive at least 1 dose of IMP (regardless of the amount of treatment administered). Patients will be analyzed for safety analyses according to the treatment actually received. For a patient randomized to a SAR425899 treatment arm, the patient will be analyzed in the treatment he/she receives starting Week 8 visit (inclusive) when no adjustment of dose level is allowed. However, for a patient randomized to a SAR425899 treatment arm and discontinues the IMP before Week 8 visit, the patient will be analyzed in the SAR425899 treatment arm the patient is randomized to. If a patient is exposed to more than one dose level of SAR425899 since Week 8 visit or later, then the patient will be analyzed in the dose level administered on Week 8 visit or study day 56 if Week 8 visit is not available. If a patient is treated with both placebo and SAR425899 any time during the study, the patient will be analyzed in the SAR425899 treatment arm. Liraglutide patients will be included in the Liraglutide treatment arm regardless of dose amount patients receive.

In addition:

- Nonrandomized but treated patients will not be part of the safety population; however, their safety data will be presented separately;

- Randomized patients for whom it is unclear whether they took the IMP will be included in the safety population as randomized;
- Patients will be excluded from the safety population only if there is documented evidence (ie, all study dates recorded as no medication taken) that patients have not taken the study medication.

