### *General common rules*

All safety analyses will be performed on the safety population as defined in [Section 2.3.2](#), unless otherwise specified, using the following common rules:

- Safety data in patients who do not belong to the safety population (eg, exposed but not randomized) will be listed separately;
- The baseline value is defined as the last available value before the first injection of IMP.
- The PCSA values are defined as abnormal values considered medically important by the Sponsor according to predefined criteria/thresholds based on literature review and defined by the Sponsor for clinical laboratory tests, vital signs, and ECG (PCSA version dated May 2014 [[Appendix A](#)]).
- PCSA criteria will determine which patients had at least 1 PCSA during the TEAE period, taking into account all evaluations performed during the TEAE period, including unscheduled or repeated evaluations. The number of all such patients will be the numerator for the treatment-emergent PCSA percentage;
- The treatment-emergent PCSA denominator by group for a given parameter will be based on the number of patients assessed for that given parameter during the TEAE period by treatment group in the safety population;
- For laboratory parameters cited in the protocol as efficacy endpoints (including HbA1c and plasma glucose), PCSA summaries will not be provided. These parameters will be summarized in [Section 2.4.4](#);
- For quantitative safety parameters based on central laboratory/reading measurements, descriptive statistics will be used to summarize results and change from baseline values by visit and treatment group. Summaries will include the last on-treatment value (see [Section 2.4.5.4](#));
- The analysis of the safety variables will be essentially descriptive and no systematic testing is planned. Relative risks versus placebo and their 95% CIs may be provided, if relevant;
- Selected safety analyses will be summarized by age group (<50, ≥50 to <65, ≥65 to <75, ≥75 years of age), gender, race subgroups, and any pertinent subgroups as appropriate (see details in [Section 2.4.5.1](#) and [Section 2.4.5.2](#)).

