## ***Analysis of pre-treatment and post-treatment adverse events***

- All pre-treatment AEs by primary SOC and PT, showing the number (%) of patients with at least 1 pre-treatment AE, sorted by the internationally agreed SOC order and decreasing incidence of PTs within each SOC in the SAR425899 0.20 mg group.
- All post-treatment AEs by primary SOC and PT, showing the number (%) of patients with at least 1 post-treatment AE, sorted by the internationally agreed SOC order and decreasing incidence of PTs within each SOC in the SAR425899 0.20 mg group.

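### TEAE and treatment-emergent SAE tables use crude percentages of all treated patients although counting stops 3 days after each patient's last dose, so unequal discontinuation would distort comparisons between arms

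*SAP*

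**What the plan says.** SAP 2.4.5.2 (Generalities) fixes the basis of the AE incidence tables: "The denominator for computation of percentages is the safety population within each treatment group". Under SAP 2.3.2, one dose is enough to enter that population. The TEAE overview, the tables by SOC and PT, the common-PT tables and the treatment-emergent SAE tables all show the number and percentage of patients.

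The window for a TEAE depends on the patient. Protocol 9.2.2.1 sets it as "from the first injection of IMP up to 3 days (1 day for hypoglycemia) after the last injection of IMP", and SAP 2.1.4 (Observation period) agrees.

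Follow-up does not end when the window closes. Protocol 10.4.3 states: "When treatment is prematurely discontinued, the patient's observations will continue until the end of the study". Events after the window go into a separate table: "All post-treatment AEs by primary SOC and PT, showing the number (%) of patients with at least 1 post-treatment AE".

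Patient-year rates are planned for hypoglycemia only (SAP 2.4.5.1; Protocol 11.4.3.1). Onset curves are planned for nausea, vomiting and severe or documented symptomatic hypoglycemia. Cumulative exposure in patient-years is reported (SAP 2.4.3.1) but is not used as a denominator for other AEs. On comparisons between groups, SAP 2.4.5 says: "Relative risks versus placebo and their 95% CIs may be provided, if relevant".

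**The concern.** A crude percentage compares arms fairly when patients in each arm are observed for similar lengths of time. Here observation ends with dosing. Protocol 8.1.1 makes intolerance a route to stopping IMP, so it is plausible that SAR425899 patients stop more often than placebo patients. An arm with more stopping would contribute less counted time over the same denominator. Events spread over the 26 weeks would then look rarer in that arm than they are per unit of treatment.

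The post-treatment table does not repair this. A completer has almost no time in it, whereas someone who stops early can have months. In the text available, only deaths have an explicit on-study count (SAP 2.4.5.3). No AE table gives every arm the same window from first dose to Week 26.

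Safety is a main secondary objective of this dose-ranging study, so an artefact that flatters a poorly tolerated arm would bear on what the study is meant to show.

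**Working it through.** The documents state no figure on this point, so there is none to reproduce.

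**Inputs from the documents:** 26 weeks of treatment; window ending 3 days (3/7 week) after last dose; 60 patients per SAR425899 arm and 30 on pooled placebo.

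**Assumptions:** 10% placebo risk over 26 weeks; constant hazard; true hazard ratio 1.5; a fraction q of the arm stopping at week s, with 20%, 30% or 40% on SAR425899 against 5%, 10% or 10% on placebo. Placebo stops at Week 13 throughout. The 3 extra days for completers are ignored.

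**Step 1, hazard.** λ = −ln(0.90)/26 = 0.00405 per week on placebo, and 1.5λ on SAR425899.

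**Step 2, full-adherence benchmark.** SAR425899 risk = 1 − 0.90^1.5 = 14.62%. RR = 14.62/10.00 = 1.46.

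**Step 3, crude TEAE risk.** With w = s + 3/7 and h the arm's hazard:

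crude = (1 − q)(1 − e^(−26h)) + q(1 − e^(−hw))

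A SAR425899 patient who stops at Week 6 (w = 6.43) has a counted risk of 3.83%, and at Week 13 (w = 13.43) 7.84%. A placebo patient who stops at Week 13 has 5.30%.

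Worked case, 30% stopping at Week 6 against 10% on placebo:
- SAR425899: 0.7 × 14.62 + 0.3 × 3.83 = 11.38%
- placebo: 0.9 × 10.00 + 0.1 × 5.30 = 9.53%
- crude RR: 11.38/9.53 = 1.19

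**Step 4, on-study risk if the excess hazard ends with the window.** For SAR425899:

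on-study = (1 − q)(1 − e^(−26 × 1.5λ)) + q(1 − e^(−1.5λw − λ(26 − w)))

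The placebo on-study risk is 10% whatever the stopping. In the worked case this gives 13.58/10.00 = 1.36.

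| Stopping, SAR425899 / placebo | Crude RR, both arms stop at Week 13 | Crude RR, SAR425899 stops at Week 6 | On-study RR, SAR425899 stops at Week 6 |
|---|---|---|---|
| 20% / 5% | 1.36 | 1.28 | 1.39 |
| 30% / 10% | 1.32 | 1.19 | 1.36 |
| 40% / 10% | 1.25 | 1.08 | 1.32 |

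**Step 5, patient-year rate.** Patients with a first event, divided by time at risk to first event or end of window, estimates the hazard itself. The rate ratio is 1.50 in every row.

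**Step 6, control case.** With 30% stopping at Week 6 in both arms the crude RR is 1.46, equal to the benchmark, so there is no differential bias.

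**Other stopping patterns.** Spreading SAR425899 stopping uniformly over the first 8 weeks, with 5% exponential stopping on placebo and the 10% risk taken over the 185-day window, gives crude RRs of 1.38, 1.25 and 1.13 for 10%, 20% and 30% stopping. The direction is the same.

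**The case against.** The strongest reply is that crude on-treatment percentages are a legitimate summary and contradict nothing in the plan. The SAP treats safety as descriptive, and relative risks are optional. Unequal exposure would be visible from the discontinuation curves (SAP 2.2), the exposure summaries and the AE listings, and a reader could divide the planned counts by the planned patient-years. The numbers are also small. In the worked case the shortfall against full adherence is 60 × (14.62% − 11.38%) = 1.9 patients. With expected counts of 6.8 of 60 and 2.9 of 30, the 95% CI around an RR of 1.19 is about 0.3 to 4.4. All of this stands. It makes the point a matter of presentation, but it does not give the planned tables a common window or a rate.

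Four stronger readings are tempting, and the documents do not support them:

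- **AESIs and adjudicated pancreatic and cardiovascular events are cut off at the window.** Those counts in SAP 2.4.5.2 are not worded as treatment-emergent, unlike the TEAE and SAE tables. Their period is simply not stated.
- **The whole gap to 1.46 is recoverable bias.** That benchmark assumes everyone stays exposed to Week 26. Protocol 9.2.2.1 puts 3 days at about five half-lives. If the excess hazard ends with dosing, an on-study count would show 1.39-1.32.
- **Discontinuation will rise with dose.** No rates are given. Protocol 8.1.1 allows dose reduction before Week 8, and SAP 2.3.2 groups continuing patients by the dose they receive from then on.
- **Events after stopping are lost.** They are collected and tabulated, but apart from the TEAEs.

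SAP Appendix B and the separate DMC SAP were not available for this review.

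**Conclusion.** The concern holds as a conditional one. If discontinuation differs between arms, the crude TEAE, treatment-emergent SAE and common-PT percentages, and any relative risk built on them, understate events that arise throughout treatment in the arm with more stopping. Events that occur before patients stop, such as early nausea, are little affected.

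The size rests entirely on the assumed stopping rates and times, the 10% background risk and the constant hazard. It is moderate if both arms stop at similar times and larger if SAR425899 patients stop early. For rarer events the loss would be a fraction of a patient per arm. This is not an error in the planned tables. It is a worthwhile and inexpensive addition to them.

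**What to change.** In SAP 2.4.5.2, keep the crude percentages and add:

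1. For the TEAE overview, treatment-emergent SAEs, AESIs and common PTs, a rate by treatment group: patients with a first event divided by patient-years at risk up to that event or the end of the TEAE period. This extends the hypoglycemia method of SAP 2.4.5.1, with time at risk ended at the first event.
2. For SAEs, AESIs and adjudicated pancreatic and cardiovascular events, an on-study number and percentage from first dose to scheduled Week 26, regardless of IMP discontinuation. Use the safety grouping of SAP 2.3.2, so that these columns and the TEAE columns share denominators.
3. A sentence stating the observation period for the planned AESI, pancreatic and cardiovascular counts.

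The cost is SAP wording and some extra columns, from data already collected. There are two drawbacks. The rate is easy to interpret only if the hazard is roughly constant, and the on-study count includes time off drug. Each should therefore sit beside the crude percentage and not replace it.
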